Appendix A

Background, Rationale and Context

Although the scientific premise of the EMPOWER Sitless intervention is based on research showing that sedentary behavior in aging has adverse effects on the regulation of body weight^{1,2} and functional decline^{3,4}, recent evidence^{5,6} suggests there will be considerable within-treatment variability in weight loss during the intensive phase of treatment (the first 6-months) and in weight regain from 6- to 18-months. ***For the past six years, we have been investigating whether or not there are brain-based phenotypes among aging adults that place certain individuals at high-risk for failing to lose weight when involved in structured programs of weight loss.*** Indeed, relative to older adults with a low self-reported drive to consume highly palatable foods, their high-scoring counterparts exhibited a shift in brain networks that is typical of other addictive behaviors following exposure to a short-term food restraint.⁷ Most recently, using baseline brain gray and white matter volume within a support vector machine learning model on older adults (n = 52) enrolled in an 18-month weight loss

intervention, we were able to predict classification to the lower or upper half of the weight loss distribution with an average accuracy of 72.62%; a receiver operating characteristic analysis indicated that classification performance was robust based on an area under the curve of 0.82.¹¹ In unpublished work, we have recently used functional network data and have increased prediction accuracy to 93%.

The ancillary study to EMPOWER will enable us to acquire baseline brain magnetic resonance imaging (MRI) scans on a random subset of $n = 90$ participants (EMPOWER has a total $n = 160$). We will test the robustness of the brain phenotypes identified in our existing work on an independent cohort, examining how well these phenotypes predict (a) weight loss during the first 6-month intensive phase and (b) weight regain from 6 months to 18 months of follow-up across all three treatment groups, and whether the predictive accuracy is similar between treatment groups. Furthermore, we are leveraging mobile technology in EMPOWER to collect ecological momentary assessment data on patterns of change in appetite, mood, and fatigue throughout the day both at baseline and again at the 6-month assessment following the intensive phase of treatment. A secondary aim of this ancillary study is to examine whether daily fluctuations in appetite, mood, or fatigue mediate the relationship between baseline brain phenotypes and weight loss at 6-months and/or weight regain from 6 to 18 months of follow-up.

Primary Aim: To evaluate the classification accuracy of brain phenotypes based on both structural brain MRI scans and functional brain networks to predict baseline-adjusted weight loss at 6 months and weight regain from 6 to 18 months both as a main effect across the three treatment groups as well as between the three treatment groups.

Secondary Aim: To examine whether the ability of both brain structure and functional brain networks to predict baseline-adjusted weight loss at 6 months and weight regain from 6 to 18 months across the three treatment groups as well as between the three treatment groups can be explained by variation in daily appetite, mood, and fatigue ratings assessed at both baseline and 6-months following the intensive phase of treatment.

Methods and Measures

Our main premise is that the structural features of gray matter and white matter in combination with functional brain networks constitute a brain phenotype for predicting the amount of weight that older adults lose following involvement in the intensive 6-month phase of a weight loss program and the amount of weight regained from 6 months until the 18-month closeout visit. We also hypothesize that the effects of this phenotype on weight loss and weight regain can be explained, in part, by self-regulatory failure due to daily fluctuations in appetite, mood, and fatigue.

A random subset of $n = 90$ participants (from the EMPOWER total $n = 160$) stratified by sex will be recruited for participation. All participants must be enrolled in the EMPOWER study and must not have contraindications for an MRI scan. All participants selected for this MRI sub-study will be asked to complete a separate informed consent.

Protocol for collecting brain images: imaging data will be collected after medical approval to participate in the EMPOWER parent study but before beginning the intervention. This baseline MRI scan will take place following an overnight fast by the participant. After completing a brief food craving and a regulation of eating questionnaire, participants will be positioned in the MRI scanner such that they can view an MR-compatible flat panel display positioned at the end of the MRI scanner. The screen is connected to the computer that will be used to present experimental stimuli. The scanning protocol involves a resting functional scan in which participants simply lie still with their attention

focused on a cross that appears on the display screen. Following the resting scan, there is both a food cue trial and a neutral cue trial that are randomly ordered. During the food cue trial, participants are presented with a series of words representing their favorite snack foods (these are collected prior to the MRI scan) and are asked to create an image of each food in their minds-eye and to focus on the taste, smell, and pleasure of consuming each food. For the neutral cue trial, neutral stimuli, such the word “chair”, are presented and participants are asked to create an image of each object focusing on the shape, color, texture and overall appearance of each object visualized. Visual analogue scales are presented immediately following each scan to acquire ratings of state craving for their favorite foods, a rating on positive/negative affect and, following the visualization tasks, a rating of how vivid the images appeared in their minds-eye.

Methods of data acquisition and processing: This project utilizes MRI data acquisition and processing techniques that our laboratory has used for the last decade. In brief, all scans will be performed on a research Siemens 3T Skyra MRI scanner with a 32-channel head coil utilizing our typical imaging protocol. T1 / T2 / FLAIR structural scans, a blood-oxygen-level-dependent (BOLD)-weighted resting scan, and BOLD-weighted trials of food cues and neutral cues will be collected. Diffusion Tensor Images (DTI) and Perfusion Images may also be acquired. The high-resolution (0.98 x 0.98 x 1.0 mm) T1-weighted structural scans will be acquired in the sagittal plane using a single-shot 3D MPRAGE GRAPPA2 sequence (TR = 2.3 seconds, TE = 2.99 ms, 192 slices). Both BOLD-weighted image sequences will be acquired in the axial plane using an echo-planar imaging (EPI) sequence (resolution = 4 x 4 x 4 mm, TR = 2.0 seconds, TE = 25 ms, flip angle = 75°, 35 slices per volume, 160 volumes).

Anatomical Image processing: the T1-weighted structural images will be first segmented into gray matter (GM) and white matter (WM) images using statistical parametric mapping toolbox version 12 (SPM12). Advanced normalization tools (ANTs) will then be used to warp the segmented images to standard space⁸. The warped images will be modulated with the Jacobian deformation field and masked using GM/WM masks provided by the International Consortium for Brain Mapping (<http://www.loni.usc.edu/atlasses>). Finally, the images will be smoothed using ANTs median filter with a radius of 1.5 mm. The resulting images will serve as the inputs into a support vector classifier in order to classify subjects in the low and high weight loss groups.

BOLD-weighted Scans: The resting state and food cue and neutral cue functional images will be processed using our typical protocol of realignment, slice-time correction, co-registration to the structural image, normalization, global signal adjustment, regression of signal from the superior sagittal sinus, and motion-correction. The first 10 images of scans will be discarded to allow for signal equilibration. This will leave us with a volume of 147 time points. Functional volumes will be slice-time corrected, and then realigned to the first image. Confounding signals, including 6 rigid-body transformation parameters generated during the realignment process and 3 mean signals (whole-brain, white matter, and CSF) will be regressed out of the functional data. The inverse of the deformation field resulting from ANTs registration will be applied to transform the Yale brain atlas⁹ to each subject's native brain space. Unlike commonly used brain atlases which integrate functionally different areas into one region, the Yale atlas is a functional atlas which parcellates brain into finer functional unites (268 regions versus 90 regions of automated anatomical labeling (AAL)). Finally, the resulting atlas in the individuals' brain space will be used to extract the mean time series for each region from the preprocessed functional images. Correlation matrices will then be thresholded to maintain edge density consistency across subjects. This process ensures that comparisons between networks are of equivalent density relative to the number of network nodes. This will be done using the formula $N = K^s$ ¹⁰, with N equal to the number of nodes and K equal to average degree (number of

edges per node in the network). Networks will be thresholded at $S = 2.5$ based on work showing that brain networks fragment when $S > 3$ ¹¹ and that the reproducibility is highest with an S between 2 and 3¹². Correlation values equal to or greater than the correlation coefficient solving the threshold formula are preserved and all others set to 0 to produce undirected, weighted networks. The resulting whole-brain networks from each study participant will then serve as the basis for the machine learning algorithm testing.

Data Analysis

Support Vector Machine (SVM) Learning classification: Our recently published SVM model was developed to classify weight loss success and failure in an elderly cohort.¹³ We will apply our published SVM model to the warped GM and WM images from the high resolution structural scans of the participants in the 3 arms of this study, and this SVM will classify the participants into successful and unsuccessful weight loss. In addition, we will apply our more recent machine learning hypergraph model that uses functional brain networks of the resting state and task-based functional brain network data. In addition, we will combine GM and WM images with resting state and task-based fMRI networks in a single machine learning model to compare the performance of this model with the models trained using structural or functional data, alone. We expect that this combined model will enhance prediction accuracy.

Following this EMPOWER clinical trial, we will assess our machine learning models by determining the accuracy, sensitivity, and specificity in classifying the participants' weight loss success/failure. Similar to our published analyses, we will also perform receiver operator characteristic (ROC) analyses to investigate how efficiently the classifiers performed at different decision thresholds. ROC curves plot sensitivity versus '1-specificity' in a given classification decision threshold, and the area under the curve (AUC) is calculated to determine the effectiveness of the predictions and is considered as the best representative score to represent classification algorithm performance. The AUC will be determined for the structural, resting state fMRI brain network, and task-based fMRI networks by themselves, as well as for the analysis combining these datasets in a single model. A one-way repeated measure analysis of variance (ANOVA) will be performed to evaluate for significant differences for the AUC between the 3 types of classifiers.

Human Subject Protection

Subject Recruitment Methods

All study participants will be enrolled in the EMPOWER study and must not have contraindications for an MRI scan. All participants selected for this MRI sub-study will be asked to complete a separate informed consent.

Informed Consent

The participant will be seated in a quiet room with a copy of the consent form. After being given time to read the form, the PI or his designee will go through the document with them, and answer any questions they might have about the study. Participant consent will be documented.

Potential Study Risks

The risks associated with MRI scans are metal objects in or on the body and fear/anxiety associated with being in the MRI scanner. To reduce any risks associated with metal, we will screen all potential participants to exclude anyone with metallic or electronic implants. In addition, all individuals are screened prior to entering the MRI suite to ensure that they do not have any metallic objects on their person. This process is performed by the MRI technologist.

To reduce fear and anxiety, the participants will be fully informed of exactly what will happen during the scan session at the informed consent meeting. They will be reminded that they are allowed to stop participating in the study at any time without any adverse consequences. Throughout the scan, the participant will be in communication with the MRI technologist. They will also have an emergency squeeze ball that alerts the technologist that they want the scan stopped. Should the participant decide to stop the MRI scan before completion, they will be allowed to withdraw from the MRI portion of the study, but remain in the rest of the study.

Confidentiality and Privacy

Confidentiality will be protected by collecting only information needed to assess study outcomes, minimizing to the fullest extent possible the collection of any information that could directly identify subjects, and maintaining all study information in a secure manner. To help ensure subject privacy and confidentiality, only a unique study identifier will appear on the data collection form. Any collected participant identifying information corresponding to the unique study identifier will be maintained on a linkage file, stored separately from the data. The linkage file will be kept secure, with access limited to designated study personnel. Data and records will be kept locked and secured, with any computer data password protected. No reference to any individual participant will appear in reports, presentations, or publications that may arise from the study.

Data and Safety Monitoring

The MRI scans will be reviewed for potential abnormalities by a board certified neuroradiologist and all findings confirmed by study coinvestigator [name], MD. Although the MRI scans collected for this study will not be of diagnostic quality, they might reveal incidental findings. Participants will be notified of such findings, and their primary care physician notified if requested by the participant. In the event that the participant does not have a primary care physician, they will be referred to the appropriate clinical practitioner based on the MRI findings. Follow up clinical evaluation would be required to validate any potential findings observed in the research MRI scans. Any medical costs associated with follow-up of an incidental finding will be the responsibility of the study participant and their parents.

Reporting of Unanticipated Problems, Adverse Events or Deviations

Any unanticipated problems, serious and unexpected adverse events, deviations or protocol changes will be promptly reported by the principal investigator or designated member of the research team to the IRB and sponsor or appropriate government agency if appropriate.

References

2. Garland T, Jr., Schutz H, Chappell MA, et al. The biological control of voluntary exercise, spontaneous physical activity and daily energy expenditure in relation to obesity: human and rodent perspectives. *J Exp Biol*. 2011;214(Pt 2):206-229.

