We hypothesize that, in older adults, intervening on SB will be more effective for preventing weight regain than the conventional approach of intervening on exercise behavior. This is supported by evidence showing: 1) decreased SPA/increased SB is a consistent biological adaptation to weight loss³¹⁻³⁹ and this adaptation predicts weight regain;⁴⁰ 2) as our data show, reducing SB with a self-monitoring intervention enhances weight loss and may prevent weight regain⁴¹; 3) interventions targeting increased exercise are less tolerated and sustained over time in older, obese adults⁴²⁻⁵⁰ who may be more likely to adhere to a SB intervention; 4) initiation of exercise in older adults can lead to compensatory increases in SB,⁵¹⁻⁶⁶ thus reducing total energy expenditure and limiting its efficacy for preventing weight regain; and 5) compensatory eating occurs in many individuals who exercise,^{56,67,68} though the effects of altering SB on appetite and energy intake are not known.

Objectives

Our pilot data provide evidence that a novel, highly acceptable, behavioral intervention (SitLess) that focuses on increased awareness of SB employing accelerometry-based self-monitoring, that is reinforced with other self-regulatory strategies, improves weight loss during treatment and prevents weight regain during a short (5-month) follow-up.⁴¹ **The main goal of this study is to definitively test the efficacy of this intervention for longer-term maintenance of lost weight.** This will be an 18-month trial in up to 189 obese (BMI=30-45 kg/m²) older (65-85 years) adults randomized to one of three treatment arms, all with a caloric restriction intervention for weight loss (WL) plus: 1) moderate-intensity aerobic exercise (WL+EX); 2) a SB intervention (WL+SitLess); or

3) (WL+EX+SitLess). Participants will undergo a 9-month weight loss intervention involving a 6-month intensive phase with decreasing contact from months 7 to 9, and a minimal contact, self-managed, 9-month follow-up phase to address these **aims and hypotheses**:

Aim 1: To determine whether addition of an intervention that targets sedentary behavior to a standard WL intervention that only targets EX results in a larger 18-month reduction in body weight in older, obese adults.

Primary hypothesis: WL+EX+SitLess will have lower 18-mo body weight than either WL+EX or WL+SitLess.

Secondary hypothesis: WL+SitLess will have lower 18-mo body weight than WL+EX.

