Aim 2: To compare the effects of the interventions on volume and pattern of sedentary behavior and physical activity and determine if these factors predict weight regain during the 9-month follow-up phase.

Hypothesis: WL+EX+SitLess will have higher total physical activity energy expenditure, less sedentary behavior, more breaks in sedentary behavior, and more minutes of light and moderate-vigorous activity averaged across follow-up than either WL+EX or WL+SitLess.

Hypothesis: Irrespective of treatment arm, greater activity energy expenditure and fewer minutes of sedentary behavior after the WL phase will be predictive of less weight regain during follow-up.

Aim 3: To evaluate treatment effects on clinical outcomes (body composition, functional fitness, cardiometabolic risk, fatigue, appetite) and social cognitive measures.

Hypothesis: WL+EX+SitLess will improve these tertiary outcomes more than either WL+EX or WL+SitLess.

Methods and Measures

Study Overview: We will use a 3-group design in up to 189 older (65-85 years), obese (BMI=30-45 kg/m²), sedentary men and women, all of whom will undergo a 9-month WL intervention (6-mo intensive phase and 3-mo reduced contact phase), followed by a 9-month self-managed follow-up phase with minimal contact, to test our overall hypothesis that intervening on SB will enhance long-term WL in this age group. **The diet element of the intervention is identical across groups, but groups differ by activity intervention:** 1) structured, moderate-intensity, aerobic exercise (WL+EX); 2) intervening on SB throughout the day (WL+SitLess); or 3) (WL+EX+SitLess).

Recruitment of study participants: Our recruitment goals include: 50% women and 20% minority. We will recruit these individuals using community-based recruitment strategies, including newspaper and radio advertisements, and mass mailings. **Specific inclusion/exclusion criteria (see table) are in place to eliminate those that may be adversely affected by the interventions or that are not able to comply with the interventions.** To reduce adverse effects of dietary WL we exclude individuals that are non-obese, those with recent WL, those who have low bone density, are being treated for osteoporosis, or taking medication that may affect bone density, and/or those who have deficient levels of vitamin D (25 hydroxyvitamin D level < 20 ng/mL) who are not taking a calcium/vitamin D supplement. We also exclude anyone who cannot walk unassisted.

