refraining from food, beverages (with the exception of water), alcohol and caffeine. Before any data collection, participants provide written informed consent and complete a HIPAA authorization form in accordance with our IRB policy. At this visit, weight and height will be measured to calculate BMI. Individuals who meet the BMI criteria will undergo a medical history and a cognitive test (MoCA). The medical history (including blood pressure, review of medications, and a fasting blood draw for metabolic panel, vitamin D level, and blood cell count) will exclude those with recent history of coronary heart disease, cancer, liver or renal disease, severe pulmonary disease, gross physical impairment, uncontrolled hypertension, or any contraindications to exercise. The fasting blood profile will exclude those with uncontrolled diabetes,⁶⁹ anemia, or liver, renal, or hematological dysfunction. Individuals with abnormal results at screening will be referred to their physicians. Prior to randomization, eligible participants will be asked if they would like to participate in an MRI ancillary study. This is visit 2.1 listed in the table on page 7. Refusal to participate in the ancillary study will not exclude them from the main (parent) study. See Appendix A for details of the MRI ancillary study. Eligible participants will be randomized to treatment using a web-based randomization scheme developed by the biostatistician, stratified by sex with random block sizes.

Study Interventions

Weight Loss intervention: 9-mo WL phase—All participants will undergo a dietary WL intervention designed to elicit behavioral changes leading to decreased caloric intake sufficient to yield a ~10% loss of initial body mass. The WL intervention includes nutrition education, state-of-the-art behavioral methods for promoting WL, and strategies that optimize self-regulation.^{8, 70, 71} During the intensive phase of WL (months 1-6), participants will meet in weekly group sessions delivered by either the RD or staff trained on specific elements of the intervention with individual sessions possible on an as needed basis. These group meetings will transition to bimonthly group meetings during months 7-9 and to monthly follow-up phone/email contact during the follow-up phase (months 10-18).

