Individual goals for caloric intake will be prescribed to achieve an energy deficit of ~400 kcal/d from weight maintenance energy requirements (resting energy expenditure x activity factor of 1.3). The macronutrient goal will target an intake range of 25-30% from protein, 20-35% fat, and 45-55% carbohydrates. The education and counseling component of the intervention will emphasize instruction in making healthy, lower-calorie food choices while teaching changes in eating habits to lower caloric intake. Specific emphasis will be placed on the acquisition and use of self-management skills, particularly self-monitoring of diet and weight.

Throughout the 9-month WL phase, participants will be asked to track their food and beverage intake daily (via a paper diary or an internet-based diary) for at least the first 3 months and then on a reduced schedule as warranted. These will be reviewed weekly by the RD. In addition, body weight is measured and recorded at all group sessions. If it is evident, either through review of diet records or inadequate WL that participants are struggling to meet their WL goals or nutrient needs then they will be asked to meet with the RD for additional assessment and intervention. During the final month of the WL treatment, emphasis will be placed on transitioning to self-managed weight maintenance. Particular emphasis is placed on regular self-monitoring of body weight and discussion of how to deal with relapse.

9-mo Follow-up phase—During this phase, participants will receive a monthly phone call or email contact, for the purpose of emphasizing study adherence and continuity of self-regulatory skills for monitoring diet and body weight.

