Participants in all three groups will receive a Fitbit activity monitor, prior to the start of intervention, to assist with self-monitoring of their prescribed activity (e.g., aerobic exercise and/or decreased daily SB). As stated above, they will be encouraged to wear the Fitbit daily during the 9-month WL phase, and to wear it at least twice/week during the 9-month follow-up phase. If the monitor is lost, stolen or damaged they will be provided with a replacement. If a participant withdraws from the study, they will be asked to return the Fitbit. After completion of the last study visit, participants will be allowed to keep the Fitbit.

In addition, the study interventions require the use of a smartphone to upload data from the Fitbit and to access the study website to receive encouragement and motivation. If a participant does not own a smartphone or their smartphone is not compatible with our applications, the study will provide them with a smartphone and a phone/data plan for the length of their participation in the

study. Participants will be expected to keep the phone with them daily and to take care not to lose or damage it. Participants will be instructed that the phone is for study use only. If the phone is lost, stolen or damaged they will be provided with a replacement. If a participant withdraws from the study, they will be asked to return the smartphone and it will be deactivated immediately. After completion of the last study visit (V8), participants will return the smartphones and they will be deactivated.

Schedule of assessment visits

Assessments at baseline, after the intensive WL phase (6-months), after the entire 9-month WL intervention (9-months) and at study end (18-months) include: the primary outcome of body weight, as well as physical activity energy expenditure, light, moderate and vigorous activity minutes, and sedentary behavior minutes and breaks. The other secondary outcome assessments (RMR, physical function and measures of cardiometabolic risk) will be performed at baseline, after the intensive WL phase (6-months), and at study end (18-months) (See Table). At follow up, Visit 7 and 8 may be combined to help with participant burden and some questionnaires will be administered over the phone to limit the time in the clinic.

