12. Ecological Momentary Assessment: Increasingly researchers are recognizing the large degree of variability within the individual, and within the day, and the role this variability has on intervention efficacy. Therefore, ecological momentary assessment (EMA) will be used to study within-person and within-day interactions between sleep quality and duration (assessed via items from the Pittsburgh sleep quality inventory), feeling states (i.e., calmness, fatigue, relaxation, tiredness, assessed via items from the exercise-induced feelings inventory), affect (assessed via the feelings scale), level of hunger (assessed by asking current level of hunger), and craving for food (assessed by asking current craving for favorite meals or snack foods).

Prior to the start of the intervention and following the initial 9-month intervention period, participants will complete week-long daily assessments. These data will align with ActivPAL monitoring. Because data collected via the study EMA website are time-stamped, they will be time-matched to the hourly ActivPAL data. Participants will be instructed to complete assessments upon waking up in the morning and immediately prior to going to bed at night.

Additionally, each participant will receive up to five daily text message prompts with links to secure web-based questionnaires. Each assessment will take the average user less than two minutes to complete, and will contain all items with the exception of sleep items, which will be assessed only during the first assessment of the day.

13. A Technology survey and Intervention survey will be administered at 9 months and 18 months assessment visits to gain insight on the participants opinion of the technology and group dynamic used in this study.

Statistical Analyses

Sample size: The sample size chosen for this study (n=180; 60/group) provides >85% statistical power (with estimated 51 completers per group, see Table) to definitively test our Primary Hypothesis. In our pilot project, the adjusted mean group weight difference after 10 months (5 months of weight loss and 5 months of follow-up) was 3.6 kg (95% CI= 1.2-6.0 kg). Thus, with the longer 18-month time frame in the proposed study, we anticipate there could be a mean group

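### EMA is scheduled at baseline and 9 months in the main protocol but at baseline and 6 months in Appendix A, which leaves the timing of the mediator unsettled; secondarily, Appendix A's regain window includes three months of weight-loss treatment

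*Combined protocol and SAP*

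**What the plan says.** **EMA timing.** Study Measure(s), item 12, has one EMA week before the intervention starts and a second later: "following the initial 9-month intervention period, participants will complete week-long daily assessments". Appendix A (Background, Rationale and Context) says that the parent trial collects EMA "both at baseline and again at the 6-month assessment following the intensive phase of treatment". Its Secondary Aim names ratings at those two times as the possible explanation of both weight outcomes.

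**Weight outcomes.** Appendix A uses weight loss at 6 months and "weight regain from 6 months to 18 months of follow-up". It keeps to these two periods in its background, both aims and its statement of premise.

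**Parent timeline.** Objectives describes a "9-month weight loss intervention involving a 6-month intensive phase with decreasing contact from months 7 to 9". Under Weight Loss intervention, "These group meetings will transition to bimonthly group meetings during months 7-9", and "During the final month of the WL treatment, emphasis will be placed on transitioning to self-managed weight maintenance". Aim 2 of the parent trial is to compare activity and sedentary behavior and to "determine if these factors predict weight regain during the 9-month follow-up phase". Under Schedule of assessment visits, the measurements "after the entire 9-month WL intervention (9-months) and at study end (18-months) include: the primary outcome of body weight".

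**The concern.** A mediator has to be measured after the exposure and before the outcome that it is meant to explain. Here the exposure is the baseline scan and the outcomes are changes in weight. If the second EMA week falls at 9 months, the Secondary Aim has no 6-month ratings to use. Substituting the 9-month ratings would explain 6-month weight loss by something measured after it. Staff following item 12 would not collect the week that Appendix A relies on, and a missed EMA week cannot be recovered.

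The second issue is what the regain outcome means. A change that starts at 6 months adds whatever happens during the last three months of the intervention to what happens once participants manage on their own. The resulting quantity differs from regain in parent Aim 2, although both carry the same name.

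**Working it through.** The plan gives no figure on this point to reproduce. The check is a comparison of timelines, followed by an illustration.

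**Step 1: the two EMA schedules.**

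| Source | First EMA | Second EMA |
|---|---|---|
| Study Measure(s), item 12 | before intervention | after month 9 |
| Appendix A, background and Secondary Aim | baseline | 6 months |

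The first week agrees. The second differs by 9 − 6 = 3 months.

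**Step 2: each possible second EMA week against each outcome.**

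| Outcome | EMA at 6 months | EMA at 9 months |
|---|---|---|
| Weight loss, 0-6 months | concurrent with the end of the outcome | 3 months after it has ended |
| Weight change, 6-18 months | at its start | 3 of 12 months (25%) already elapsed |
| Weight change, 9-18 months | 3 months before its start | at its start |

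Neither schedule puts the second EMA week before 6-month weight loss. A 6-month week is in order for change after 6 months, and a 9-month week only for change after 9 months.

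**Step 3: the regain window.** Appendix A's window is 18 − 6 = 12 months. The intervention runs to month 9, so 9 − 6 = 3 months, or 3/12 = 25% of the window, lie inside it. The follow-up phase named in Aim 2 is 18 − 9 = 9 months. The 25% is a share of calendar time and not a measure of bias.

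A hypothetical case shows the difference in meaning. A participant who loses 3 kg in months 7-9 and regains 4 kg in months 10-18 has a 6-18 month change of −3 + 4 = +1 kg and a 9-18 month change of +4 kg.

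**Step 4: how far the two quantities could diverge (illustration only).** The documents give no SDs for 6-9 or 9-18 month change. Let r be the ratio of the first SD to the second, and c the correlation between the two changes. Then

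corr(6-18 change, 9-18 change) = (1 + c·r) / √(1 + r² + 2·c·r).

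Under bivariate normality, the share of participants who fall on different sides of a median split is arccos(corr)/π.

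| r | c | corr | different half |
|---|---|---|---|
| 0.3 | 0 | 1/√1.09 = 0.958 | 9.3% |
| 1.0 | 0 | 1/√2 = 0.707 | 25.0% |
| 0.3 | +0.3 | 0.967 | 8.2% |
| 1.0 | −0.3 | 0.7/√1.4 = 0.592 | 29.8% |

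The assumed range of r is 0.3 to 1.0. With c = 0 the share is about 9% to 25%; with c between −0.3 and +0.3 it is about 8% to 30%. The median split is also an assumption. The earlier model described in Appendix A used halves of the weight-loss distribution, but no cut-point is stated for regain.

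**The case against.** On EMA, the defence is that the slip may lie in item 12 and not in the appendix. Item 12 aligns EMA with ActivPAL monitoring, and activity is assessed at 6 months as well as at 9. The visit table that could settle the matter is not in the text available for this review. This stands as a limit: the documents do not show which schedule was intended. A reader might infer that the mediator is missing altogether. They do not support that, because baseline EMA is in both texts and only the second week is in doubt, and then only if item 12 governs. Correcting item 12 to 6 months would not rescue the whole aim either, because a 6-month rating coincides with the 6-month weight outcome.

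On the window, the defence is stronger. Appendix A uses 6-18 months consistently and ties it to the end of the intensive phase, a milestone that the parent trial also assesses. The parent's own Data analyses section uses 6-month activity to predict regain at 18 months without saying where regain starts. Contact thins out after month 6, so regain could begin then, and a 9-18 month window would miss it. Moving the start to 9 months while weight loss ends at 6 would leave months 7-9 in neither outcome. All of this stands, and it makes the window a matter of naming and justification rather than an error. A reader might also infer that participants are misclassified as low regainers. That is not supported: the appendix defines no regain classes, its classification methods concern weight-loss success, and no data on 6-9 month weight change are given.

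**Conclusion.** The EMA contradiction is firm and rests on the text alone: two sections give different times, 3 months apart, for the same second assessment. Under either reading, post-baseline EMA cannot support a mediation claim for 6-month weight loss. Under the 9-month reading, it also fails to precede the whole of the 6-18 month outcome.

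The window point carries less weight. The 6-18 month quantity is net weight change after the intensive phase, with 3 of its 12 months under continuing though reduced treatment, and it does not match the regain of parent Aim 2. Its practical effect is unknown; the 8% to 30% range depends wholly on assumed SDs, correlations and a median split.

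Both points are confined to the ancillary MRI study, and the firm one to its Secondary Aim. The parent trial's primary comparison of 18-month weight is not affected.

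**What to change.** 1. **Reconcile item 12 with Appendix A** so that both give the same time for the second EMA week.
   - *If it stays at 9 months:* limit mediation by post-baseline EMA to 9-18 month weight change and drop it for 6-month weight loss. The cost is the loss of that claim.
   - *If it is at 6 months:* correct item 12, use the 6-month ratings as a mediator only for weight change after 6 months, and report their link with 6-month weight loss as concurrent. The cost is a wording change and, if the week is not already being collected, an EMA week at 6 months, where activity is already assessed.
2. **Name the 6-18 month outcome for what it is.** Describe it as net weight change after the intensive phase, with a sentence of justification, and add a 9-18 month regain analysis that matches parent Aim 2. Reporting both keeps months 7-9 from falling outside every outcome. The cost is appendix wording and one further analysis; the 9-month weight is already measured, so no visit is added.
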